## STATEMENT OF COMPLIANCE

The trial will be carried out in accordance with International Council on Harmonization Good Clinical Practice (ICH GCP) and the following:

- United States (US) Code of Federal Regulations (CFR) applicable to clinical studies (45 CFR Part 46, 21 CFR Part 50, 21 CFR Part 56, 21 CFR Part 312, and/or 21 CFR Part 812).

National Institutes of Health (NIH)-funded investigators and clinical trial site staff who are responsible for the conduct, management, or oversight of NIH-funded clinical trials have completed Human Subjects Protection and ICH GCP Training.

The protocol, informed consent form(s), recruitment materials, and all participant materials will be submitted to the IRB for review and approval. Approval of both the protocol and the consent form(s) must be obtained before any participant is consented. Any amendment to the protocol will require review and approval by the IRB before the changes are implemented to the study. All changes to the consent form(s) will be IRB approved; a determination will be made regarding whether a new consent needs to be obtained from participants who provided consent, using a previously approved consent form.

## 1 PROTOCOL SUMMARY

[figure not shown]
### 1.1 SYNOPSIS

|                            |   |
|----------------------------|---|
| Title:              | Palliative Care for Persons with Late-stage Alzheimer's and Related Dementias and their Caregivers: A Randomized Clinical Trial   |
| Grant Number:       | R01AG065394   |
| Study Description:  | This study is a multi-site RCT of the ADRD-PC program of dementia-specific palliative and transitional care for people with late-stage ADRD and their caregivers.   |
| Objectives:         | 
Aim 1: To conduct a multi-site RCT of the ADRD-PC program (intervention arm) vs publicly available educational material for dementia caregivers (control arm) to compare 60-day hospital transfers (hospitalization and emergency room visits) for persons with late-stage ADRD (primary outcome).
 
Aim 2: To compare patient-centered secondary outcomes between intervention and control arms: a) symptom treatment; b) symptom control; c) post-acute use of community palliative care or hospice; and d) new nursing home transitions.
 
Aim 3: To compare caregiver-centered secondary outcomes between intervention and control arms: a) communication about prognosis and goals of care; b) shared decision-making; and c) caregiver distress.
 |
| Endpoint/ Outcomes: | 60-day hospital transfers (Aim 1, primary outcome).
Patient-centered secondary outcomes (Aim 2); a) symptom treatment (Palliative Care Domain index); b) symptom control (Symptom Management at the End of Life in Dementia scale, Neuropsychiatric Inventory Questionnaire); c) post-acute use of community palliative care or hospice; and d) new nursing home transitions.
Caregiver-centered secondary outcomes (Aim 3); a) communication about prognosis and goals of care; b) shared decision-making; and c) caregiver distress (Family Distress in Advanced Dementia scale, Zarit Burden short form).  |
| Study Population:   | 424 dyads of hospitalized patients with late-stage ADRD and their family caregivers and 50 dyads of hospitalized patients with late-stage ADRD and their family caregivers who identify as Hispanic/Latino  |
| Phase or Stage:     | NIA Behavioral Intervention Efficacy trial (Stage II)   |

|   |   |
|---|---|
| Description of Sites/Facilities    | 5 medical centers with interdisciplinary specialty palliative care teams - University of North Carolina (UNC), University of Indiana (IU), University of Colorado (UC), Massachusetts General Hospital (MGH), Emory University (EU) |
| Description of Study Intervention: | The ADRD-PC program includes 3 main components: dementia-specific palliative care consultation, standardized caregiver education, elements of evidence-based transitional care.   |
| Study Duration:                    | 60 months   |
| Participant Duration:              | 60 days post hospitalization  |

## SCHEMA

## Flow Diagram

## 1.2 SCHEDULE OF ACTIVITIES

|  | Visit 1: During Hospitalization | Visit 2: During Hospitalization (Intervention) | Visit 3: PC Call 72 hours after discharge (Intervention) | Visit 4: PC Call 2 weeks after discharge (Intervention) | Visit 5 CRC interview 30 days post Hospitalization | Visit 6 CRC interview 60 days post hospitalization | CRC EHR Review post-60-day Hospitalization |
|--|---------------------------------|--|--|---|--|--|--|
| STUDY ENROLLMENT ACTIVITIES                                   |                                 |  |  |   |  |  |  |
| EHR Eligibility Screen   | X                               |  |  |   |  |  |  |
| Informed Consent   | X                               |  |  |   |  |  |  |
| Enrollment Baseline Assessment                                       | X                               |  |  |   |  |  |  |
| Randomization  | X                               |  |  |   |  |  |  |
| Control arm  | X                               |  |  |   | X  | X  | X  |
| ADRD-PC intervention arm   | X                               | X  | X  | X   | X  | X  | X  |
| DATA COLLECTION ACTIVITIES                                    |                                 |  |  |   |  |  |  |
| Hospital / ED transfers  |                                 |  |  |   | X  | X  | X  |
| Palliative Care Domain Index   |                                 |  |  |   |  |  | X  |
| Symptom Management at the End of Life in Dementia (SM-EOLD)          |                                 |  |  |   | X  | X  |  |
| Neuropsychiatric Inventory Questionnaire (NPI-Q)                     |                                 |  |  |   | X  | X  |  |
| Post-acute use of palliative care, hospice                           |                                 |  |  |   | X  | X  |  |
| New NH transition  |                                 |  |  |   |  |  | X  |
| Documented discussion of dementia prognosis                          |                                 |  |  |   |  |  | X  |
| Documented decision-making for goals of care                         |                                 |  |  |   |  |  | X  |
| Shared decision-making about hospitalization & burdensome treatments |                                 |  |  |   | X  | X  |  |
| Family Distress in Advanced Dementia scale                           |                                 |  |  |   | X  | X  |  |
| Zarit Burden scale   |                                 |  |  |   | X  | X  |  |

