### 6.3 MEASURES TO MINIMIZE BIAS: RANDOMIZATION AND MASKING

Randomization will occur following the enrollment interview, with the dyad as the unit of randomization and analysis. Allocation will be concealed prior to randomization. Randomization will be generated within REDCap software, and transmitted by the Site-CRC to the PC team to initiate ADRD-PC (intervention) or to deliver dementia caregiver educational material (control).

CRCs who collect outcome data will be masked to study arm in family caregiver interviews. Since the EHR will have ADRD-PC palliative care encounters, Site-CRCs will complete follow-up EHR reviews only after 60-day follow-up interviews. [name] (PI) will remain masked to study arm assignments to minimize bias in study procedures and analysis.

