## 8 STUDY ASSESSMENTS AND PROCEDURES

## 8.1 ENDPOINT AND OTHER NON-SAFETY ASSESSMENTS

Data collection will be identical for both arms. Data will be obtained from caregiver enrollment interviews and 30- and 60-day interviews post-discharge, and from electronic health record (EHR) reviews encompassing the 60-day period post-hospitalization. Based on the pilot RCT, we estimate 10% of persons with late-stage ADRD will die during follow-up; caregiver interview data collection will proceed using a Bereavement Interview adaptation. Outcome measures will focus on 60-day interviews; 30-day interim interviews are necessary to support retention, ensure data capture for persons with ADRD who die, and for valid recall of hospital transfers (primary outcome) and secondary outcomes.

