**Table 3: Power for Comparing Intervention and Control Arms Based upon the Study Design**

| Aim       | Measure                                   | Control | SD  | Difference | Power, 15% dropout | Power, 25% dropout |
|-----------|---|---------|-----|------------|--------------------|--------------------|
| 1  | 60-day hospital transfers (Poisson rate)  | 0.53    | --  | 0.25, 0.2  | 0.96, 0.82         | 0.95, 0.79         |
|           | 60-day hospital transfers (overdispersed) | 0.53    | --  | 0.25, 0.2  | 0.81, 0.60         | 0.76, 0.55         |
| 2a | PC Domain Index (0-10)                    | 2.7     | 1.7 | 5, 0.5     | >0.99, 0.80        | >0.99, 0.75        |
| 2b | 60-day hospice use (%)                    | 3%      | --  | 22%,8%     | >0.99, 0.85        | >0.99,0.80         |
| 2c | Symptom distress (SM-EOLD)                | 36.4    | 7.8 | 4, 2.3     | >0.99, 0.80        | >0.99, 0.75        |
| 2d | Transition to nursing home care (%)       | 33%     | --  | 30%,15%    | >0.99, 0.82        | >0.99, 0.78        |
| 3a | Discussion of dementia prognosis          | 3%      | --  | 87%, 8%    | >0.99, 0.85        | >0.99, 0.80        |
| 3a | Discussion of goals of care (%)           | 25%     | --  | 65%,14%    | >0.99, 0.82        | >0.99, 0.77        |
| 3b | Decision-making about hospitalization     | 0%      | --  | 13%, 4%    | >0.99, 0.78        | >0.99, 0.73        |
| 3b | Decision-making about treatments          | 6%      | --  | 47%, 9%    | >0.99, 0.80        | >0.99, 0.75        |
| 3c | Family Distress in Advanced Dementia      | 2.4     | 0.5 | 0.15, 0.1  | 0.81, 0.47         | 0.76, 0.43         |

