#### 9.4.3 ANALYSIS OF THE SECONDARY ENDPOINT(S)

**Aim 2:** To compare patient-centered secondary outcomes between intervention and control arms: a) symptom treatment (Palliative Care Domain index); b) symptom control (Symptom Management at the End of Life in Dementia scale, Neuropsychiatric Inventory Questionnaire); c) post-acute use of palliative care or hospice; and d) transition to nursing home care.

Analysis to Meet Aim 2: We will compare study arms during 60 days post-discharge on the following outcomes:

2.a. Symptom treatment: This ordinal outcome is the summation of presence (=1) or absence (=0) of 10 domains of palliative care. We will treat it as a continuous variable due to a high variation observed in the pilot data. We will use Student's t-test to compare the mean difference between study arms unless violation of assumptions warrants the Mann-Whitney test. We will use a multiple linear regression model with main effects for treatment group, study site, GDS Stage and patient and caregiver sex as a biological variable.

2.b. Symptom control: We will use Symptom Management (SM-EOLD) scale to measure caregiver report of patients' uncontrolled symptom distress and Neuropsychiatric Inventory Questionnaire (NPI-Q) to measure caregiver report of patients' neuropsychiatric symptom distress. Linear mixed models with random intercepts for patients will be used with a time indicator (30 vs 60 days follow-up) with the above main effects.

2.c. Use of post-acute palliative care or hospice: This outcome will be defined by whether patients ever use hospice or outpatient palliative care during the time from discharge to 60 days follow-up. We will compare the proportions using Pearson's chi-square test. Logistic regression will be used for multivariable modeling with the same main effects as in Aim 2.a. Final estimates will be reported as covariate-adjusted odds ratios.

2.d. Transition to nursing home care: This outcome will be defined by whether patients transition to nursing home care during the time from discharge to 60 days follow-up. We will compare proportions using Pearson's chi-square test. Logistic regression will be used for multivariable modeling with the same main effects as in Aim 1. Final estimates will be reported as covariate-adjusted odds ratios.

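### No baseline caregiver distress (FDAD) or burden (Zarit) score is scheduled or specified as a covariate, so the secondary outcome with the lowest power in Table 3 gives up precision that an existing pre-randomization interview could supply

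*Combined protocol and SAP*

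**What the plan says.** - **Timing.** In Section 1.2 the row for the "Family Distress in Advanced Dementia scale" (FDAD) reads "Family Distress in Advanced Dementia scale | | | | | X | X" and the Zarit row reads "Zarit Burden scale | | | | | X | X": marks under the 30- and 60-day interviews, none under Visit 1. The same table has a Visit 1 line, "Enrollment Baseline Assessment", whose instruments are not given.
- **A pre-randomization contact exists.** Section 6.3: "Randomization will occur following the enrollment interview, with the dyad as the unit of randomization and analysis". Section 8.1: "Data will be obtained from caregiver enrollment interviews and 30- and 60-day interviews post-discharge". Section 8.1 also lists both scales under the caregiver interviews, without saying at which interview.
- **Analysis.** For Aim 3c, Section 9.4.3 gives a t-test on FDAD and then the model of Aim 2.b: "Linear mixed models with random intercepts for patients will be used with a time indicator". Its other terms are treatment, site, GDS stage, and patient and caregiver sex. No baseline score appears. Zarit is named in the aim, but the analysis text spells out only FDAD; I take the same models to apply to both.
- **Other route for a covariate.** Section 9.4.1 brings in a baseline variable only if it differs between arms, and keeps it only if removing it appreciably changes the treatment coefficient.
- **Power.** The Table 3 row "Family Distress in Advanced Dementia" has control mean 2.4, SD 0.5, differences 0.15 and 0.1, and power 0.81 and 0.47 (15% dropout) or 0.76 and 0.43 (25%).

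**The concern.** A score taken before randomization cannot be affected by treatment. To the extent that it predicts the follow-up score, adjusting for it removes residual variance without another dyad. The plan has the interview at which to take the score, but neither schedules it nor commits to using it.

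This matters most for FDAD. At the larger difference every other secondary row in Table 3 exceeds 0.99. At the smaller difference the next lowest row is 0.78 (15% dropout) and 0.73 (25%), against 0.47 and 0.43 for FDAD.

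The rule in Section 9.4.1 does not fill the gap. It screens for confounding, not for prognostic value. A baseline distress score that happened to be balanced would be left out however well it predicted the outcome, and a score that was not collected cannot be screened at all.

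**Working it through.** **Inputs from the documents.** SD 0.5 and differences 0.15 and 0.10 (Table 3); 180 per arm at 15% dropout, 159 at 25%, two-sided alpha 0.05 (Section 9.2).

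**Inputs assumed.** The documents give no correlation for FDAD over time. I take the baseline to follow-up correlation r_b from 0.3 to 0.7, and the 30-to-60-day correlation r_f as 0.5 or 0.7. The SD is taken as equal at every time, with both follow-ups complete.

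**Step 1: reproduce Table 3.** SE = SD × √(2/n); power ≈ Φ(difference/SE − 1.96).

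- n = 180: SE = 0.5 × √(2/180) = 0.0527. For 0.15: 0.15/0.0527 = 2.85, power 0.812. For 0.10: 1.90, power 0.475.
- n = 159: SE = 0.0561, power 0.763 and 0.430.

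All four stated values (0.81, 0.47, 0.76, 0.43) are recovered. Table 3 therefore describes an unadjusted comparison at one visit.

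**Step 2: add a baseline covariate to the single-visit comparison.** Residual SD = 0.5 × √(1 − r_b²). Example for r_b = 0.5, n = 180: residual SD 0.433, SE 0.0456, 0.15/0.0456 = 3.29, power 0.908.

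| r_b | Variance removed | n=180: 0.15 / 0.10 | n=159: 0.15 / 0.10 | Difference detectable at 80% power, n=180 |
|---|---|---|---|---|
| none | 0 | 0.812 / 0.475 | 0.763 / 0.430 | 0.148 |
| 0.3 | 9% | 0.847 / 0.512 | 0.801 / 0.464 | 0.141 |
| 0.5 | 25% | 0.908 / 0.591 | 0.870 / 0.539 | 0.128 |
| 0.7 | 49% | 0.979 / 0.757 | 0.963 / 0.704 | 0.105 |

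For the 0.10 difference to reach 80% at one visit, r_b would have to be about 0.74 at n = 180.

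**Step 3: the planned mixed model.** Section 9.4.3 lists main effects and time, with no treatment-by-time term, so the treatment effect is averaged over the two visits. The mean of two visits has variance SD² × (1 + r_f)/2. A baseline score with correlation r_b to each visit removes SD² × r_b². The residual variance is SD² × [(1 + r_f)/2 − r_b²].

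Power at n = 180, for 0.15 / 0.10:

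| r_b | r_f = 0.5 | r_f = 0.7 |
|---|---|---|
| none | 0.908 / 0.591 | 0.870 / 0.539 |
| 0.3 | 0.939 / 0.646 | 0.904 / 0.586 |
| 0.5 | 0.981 / 0.765 | 0.957 / 0.688 |

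Example for r_f = 0.5, r_b = 0.3: factor 0.75 − 0.09 = 0.66, SD = 0.5 × √0.66 = 0.406, SE = 0.0428, 0.15/0.0428 = 3.50, power 0.939.

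Against this model, r_b = 0.3 adds about 3 to 6 points. With r_b = 0.5 the gain is about 7 to 9 points for 0.15 and 15 to 17 points for 0.10.

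**The case against.** **The scales may already be asked at enrollment.** This stands. The enrollment assessment is not itemized, Section 8.1 lists both scales without timing, and Section 9.4.1 refers to unlisted baseline measures. A reader might infer from the schedule that distress is measured only after discharge. The documents support no more than that no baseline score is scheduled or specified.

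**Table 3 understates the planned analysis.** This also stands. A reader might take 0.81 and 0.47 as the power of the Aim 3c mixed model and credit the whole rise in Step 2 to a baseline covariate. Those figures belong to a one-visit t-test. Averaging two visits already recovers part of the gap, and the baseline gain should be judged from there.

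**The correlation is unknown and could be low.** This stands as a limit on size. The score would be taken during an acute hospitalization, and about 10% of patients are expected to die, after which an adapted bereavement interview is used (Section 8.1). At 0.3 the gain is small.

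**More questions burden a stressed caregiver.** Section 2.3.1 names emotional distress as the primary caregiver risk, and Section 5.2 excludes dyads who would be unduly stressed. A short enrollment interview is a defensible choice, though the documents do not give this as the reason. The objection disappears if the scales are already asked there.

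None of this explains why a baseline score, if available, should enter only through the imbalance and change-in-effect rule.

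**Conclusion.** The point holds as an inexpensive, optional improvement. A baseline FDAD or Zarit score is neither scheduled nor pre-specified as a covariate, and the rule in Section 9.4.1 would not secure its benefit.

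The size depends on correlations that the documents do not give. Over 0.3 to 0.7, single-visit power at 180 per arm would be 0.85–0.98 for 0.15 and 0.51–0.76 for 0.10. The mixed-model gain ranges from a few points to a substantial improvement for the smaller difference.

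A reader might infer that the Aim 3c comparison is biased or invalid. It is not: randomization protects it, and only precision is at stake, on a secondary outcome. Nor does the low-power statement extend to Zarit, which has no row in Table 3. SM-EOLD and NPI-Q show the same gap in the schedule.

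**What to change.** 1. In Section 1.2, mark FDAD and the short-form Zarit at Visit 1, before randomization. If they are already asked there, the mark alone is enough. Listing the enrollment instruments would settle the question.
2. In Section 9.4.3, name the baseline score of the same scale as a covariate in the Aim 3c mixed models, and state that it stays in regardless of balance or change in the treatment coefficient.
3. Decide whether SM-EOLD and NPI-Q should be handled the same way.

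**Cost.** A few more minutes in an interview that already takes place, and one term per model. The drawback is added burden on a caregiver in a stressful setting; the right to skip items in Section 2.3.1 applies. If enrollment is under way and the scales were not asked, earlier dyads will have no baseline score, and the plan should say how those missing values are handled.

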## 2 INTRODUCTION

### 2.1 STUDY RATIONALE

Alzheimer's disease and related dementias (ADRD) are progressive and incurable. ADRD affects 5.6 million Americans at an annual cost of \$157 billion. Approximately 3 million Americans are living with late-stage, or moderately severe to advanced dementia. They suffer with progressive dependency, loss of awareness of self and family, and escalating physical and neuropsychiatric symptoms. ADRD also adversely affects families; caregivers for late-stage ADRD experience marked physical, emotional, and financial strain.

Hospitalizations present a unique opportunity for dementia-specific palliative care, since 72% of hospitals have interdisciplinary palliative care teams. Palliative care improves symptom control and quality of life in serious illnesses, but has never been adapted and tested for the unique needs of late-stage ADRD.

We have therefore designed the **ADRD Palliative Care (ADRD-PC)** program of dementia-specific palliative and transitional care, and demonstrated its feasibility and potential efficacy. We now propose a rigorous multi-site efficacy clinical trial of ADRD-PC.

### 2.2 BACKGROUND

Alzheimer's disease and related dementias (ADRD) have unprecedented public health impact. ADRD affects 5.6 million Americans and their family caregivers; 3 million live with late-stage ADRD. The prevalence and incidence of ADRD is increased for under-represented minority populations, who are in turn a growing proportion of the US population. Annual dementia care costs exceed \$157 billion. ADRD contributes to 1 in 3 deaths over age 65, and is the only major cause of death with no clinically relevant treatment to prevent, cure or slow disease progression.

Current care demonstrates unmet needs for palliative care. People with late-stage ADRD suffer progressive dependency and distressing symptoms, and their family caregivers experience physical, emotional, and financial strain. Healthcare disparities magnify symptoms and suffering associated with late-stage ADRD, and Hispanic / Latino families provide more intensive caregiving compared to White Americans. Clinical care is highly fragmented, with frequent transitions between home, emergency department, hospital, and nursing facilities. Persons with late-stage ADRD become "healthcare nomads," experiencing frequent burdensome transitions between hospitals and home or facility care. Acute illness hospitalizations for infections, injurious falls, or dehydration worsen physical and neuropsychiatric symptoms, and trigger decisions about goals of care and intensive treatments. Acute illness hospitalizations are burdensome, yet 23-47% are potentially avoidable.

Palliative care is rare for ADRD, and no major RCT tests dementia-specific palliative care. Persons with ADRD and their caregivers have unique palliative care needs that do not match standard models of palliative care. Culturally adapted ADRD care is needed, but interventions are rarely designed or adapted. Palliative care clinicians lack training in dementia-specific skills, and rarely see persons with ADRD. Our research team completed two pilot trials demonstrating feasibility and potential efficacy of the ADRD-PC program. Thus, the necessary next step to advance the science of dementia-specific palliative care is an adequately powered efficacy RCT of the ADRD-PC program to improve patient and caregiver outcomes. Research responds to the National Alzheimer's Project Act, Alzheimer's Association guidelines, and NIA priorities for

geriatric palliative care (PA-18-502) and research to improve quality of care and quality of life for persons with ADRD (PAS-18-030).

